8.4.1 Criteria for Early Termination

A subject may withdraw or be withdrawn from the study for the following reason.

- Subject withdrew consent.
- Sponsor requested subject to be withdrawn.
- Request of primary care physician or investigator.
- Protocol violation/ Non-compliance.
- Lost to follow-up/failure to return.
- Adverse Event (specify primary AE in the AE log).
- Marked disease progression as defined at any time during study drug therapy.
- The occurrence of marked progressive liver disease
- Unresolved or recurrent grade III or IV toxicity.
- Pregnancy.
- Death.
- Other.

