The sponsor must be provided with a copy of the laboratory's certification, and a tabulation of the normal ranges for each parameter required. Additionally, if at any time a patient has laboratory parameters obtained from a different outside laboratory, the sponsor must be provided with a copy of the certification and a tabulation of the normal ranges for that laboratory. At any time during the study, abnormal laboratory parameters which are clinically relevant (e.g. require dose modification and/or interruption of study drug, lead to clinical symptoms or signs or require therapeutic intervention), whether specifically requested in the protocol or not, must be recorded on the appropriate Comment CRF page in addition to the appropriate laboratory CRF page. When abnormal laboratory values or test results constitute an adverse event (i.e., induces clinical signs/ symptoms or requires therapy) they must be recorded on the Adverse Events CRF.

When, in the opinion of the investigator, other clinical laboratory evaluations may be relevant for assessing the patient's status, they will be completed and entered into the database as appropriate.

Special tests:

- Total cholesterol, HDL cholesterol, LDL cholesterol and triglycerides will be specifically determined as probable safety parameters in this study, which affect lipid metabolism.
- See Section 9.11 for additional specialty test (Exploratory Laboratory tests and other Laboratory tests needed)

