11.1 Adverse Event

An adverse event (AE) is defined as any untoward medical occurrence in a patient or clinical trial subject administered a medicinal product and which does not necessarily have a causal relationship with the treatment.

In the study, any event occurring after the clinical trial subject has signed the study Informed Consent should be recorded and reported as an AE.

An adverse event can therefore be any unfavorable and unintended sign (including an abnormal laboratory finding), symptom, or disease temporally associated with the use of an investigational medicinal product, whether or not considered related to the investigational medicinal product.

A new condition or the worsening of a pre-existing condition will be considered an AE. Stable chronic conditions such as arthritis that is present prior to study entry and do not worsen during the study will not be considered AE.

Worsening of the disease under study will be measured by laboratory test and clinical parameters should only be recorded as an AE if the outcome is more serious than would normally be expected from the normal course of the disease in a particular subject.

An abnormal result of diagnostic procedures including abnormal laboratory findings will be considered an AE if it:

- Results in subject's withdrawal by the investigator.
- Is associated with a serious adverse event (SAE).
- Is associated with clinical signs or symptoms.
- Is considered by the physician to be of clinical significance.

The intensity or severity of the AE will be characterized as:

Mild:AE which is easily tolerated.Moderate:AE sufficiently discomforting to interfere with daily activity.Severe:AE which prevents normal daily activities.

Unlabeled/ Unexpected AE - A reaction which is not included in the Adverse Reaction section of the relevant reference, including specificity, severity, outcome or frequency. The safety reference of this study is the Investigator's Brochure (IB).

TERMDEFINITIONCLARIFICATIONUnrelatedThis category applies to those
adverse events which, after
careful consideration, are

The relationship of an AE to the study drug is characterized as:

TERM	DEFINITION	CLARIFICATION
	clearly due to extraneous causes (disease, environment, etc.)	

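### Sections 10.2 and 11.1 define a laboratory adverse event differently, so an asymptomatic, untreated abnormality that is judged significant or leads to withdrawal may be missing from the AE tables

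*Combined protocol and SAP*

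**What the plan says.** Section 10.2 (Safety Laboratory Evaluations) works in two steps.

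- Clinically relevant abnormalities "must be recorded on the appropriate Comment CRF page in addition to the appropriate laboratory CRF page". The examples given are those that "require dose modification and/or interruption of study drug, lead to clinical symptoms or signs or require therapeutic intervention".
- A narrower group goes on the Adverse Events CRF: "When abnormal laboratory values or test results constitute an adverse event (i.e., induces clinical signs/ symptoms or requires therapy) they must be recorded" there.

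Section 11.1 (Adverse Event) sets its own test: "An abnormal result of diagnostic procedures including abnormal laboratory findings will be considered an AE if it" meets any of four criteria. These are that it leads to "withdrawal by the investigator", that it is associated with an SAE, that it is associated with clinical signs or symptoms, or that it "Is considered by the physician to be of clinical significance".

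Section 8.4.1 lists, among the reasons for early termination, "Adverse Event (specify primary AE in the AE log". Section 4.3.2 makes the proportion who discontinue because of AEs a tolerability measure. Section 12.9.1 plans TEAE tables by preferred term, severity, relationship, action taken and outcome, and for subjects who terminated early.

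**The concern.** In 10.2 the clinically relevant group is introduced with *e.g.* and the AE group with *i.e.*, so the second reads as a definition rather than as examples. A coordinator who uses 10.2 to decide which CRF page to complete has no instruction there to open an AE record for a silent enzyme rise that needed no therapy, even if the investigator thinks it significant or withdraws the subject because of it. A coordinator who uses 11.1 would open one.

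This kind of event is foreseeable here. Section 7.3 provides for discontinuation on suspected or confirmed hepatotoxicity. Section 7.4 reports a predicted interaction ratio of 1.9 for simvastatin with Aramchol 600 mg. ALT, AST and CPK are routine safety tests. The trial is meant to help choose the safest and most effective dose (5.2), so AE counts by arm should not depend on which section a site happened to read. The primary and key secondary efficacy analyses are not affected.

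**Working it through.** No arithmetic claim in the plan is at issue, so the check sets the two rules side by side and follows one event through them.

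| Feature of the abnormality | AE under 10.2 | AE under 11.1 | Named for the Comment page in 10.2 |
|---|---|---|---|
| Signs or symptoms | yes | yes | yes |
| Requires therapy | yes | not listed | yes |
| Withdrawal by the investigator | not listed | yes | not named |
| Associated with an SAE | not listed | yes | not named |
| Judged clinically significant | not listed | yes | not named in those words |
| Dose modification or interruption of study drug | not listed | not listed | yes |

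**Which differences matter in practice.**
- SAE association: the subject already has a reportable adverse event, so little is lost.
- Therapy alone: this needs a physician to treat an abnormality that he or she considers not clinically significant, which should be rare.
- Withdrawal or judged significance, without symptoms or therapy: this is the real gap. It is an AE under 11.1 and not under 10.2.

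**Is there a tie-break?** The only precedence rule (section 12 opening, and 12.11) puts the SAP above the protocol. The statistical text available, section 12.9.1, repeats only the general AE definition. It does not settle a conflict between two protocol sections.

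**Where the event then appears.** If the site follows 10.2, it is on the laboratory and Comment CRF pages.
- The 12.9.1 tables need an AE record, so they omit it.
- No analysis of Comment-page entries is planned in 12.9.1 to 12.9.6.
- The 4.3.2 measure depends on the termination reason. If the site chooses adverse event, 8.4.1 requires the AE in the log. If it chooses another listed reason, such as an investigator or sponsor request, the case is not counted as an AE discontinuation.

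**How much the laboratory outputs recover.** Section 12.9.2 plans tables of potentially clinically significant values (ALT and AST above 3 times ULN, CPK above 2.5 times ULN), shift tables and eDISH, from central laboratory data. Scheduled on-treatment safety laboratory tests fall at weeks 2, 4, 8, 24, 40 and 52 (section 5.1). Section 10.2 allows a local laboratory at visits 3, 4, 5 and 9, which are weeks 2, 4, 8 and 40. So 4 of the 6 visits may have no central value. A local rise at one of those visits could be absent from both the AE tables and the central-laboratory tables. Where a central value exists, these tables still do not carry relationship to study drug, action taken or outcome.

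**Size.** Events missing = (events of this kind) × (share handled under 10.2 alone). The documents give neither factor. The share can lie anywhere from 0, if every site applies 11.1, to 1, if every site applies 10.2.

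**The case against.** The best defence is that 11.1 is the protocol's AE definition and 10.2 is only about handling laboratory results. Section 11.1 also says in general terms that an abnormal laboratory finding can be an AE. Section 10.2 contains no *only* and does not forbid further AE entries, so a site that applies 11.1 complies with both. This is a reasonable reading, and it is why the loss is possible and not certain. But nothing directs a site to it, and 10.2 is the passage that says which CRF page to complete.

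A reader might infer three stronger things that the documents do not support.

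- *That the Comment page replaces the AE form.* It does not. Every clinically relevant abnormality goes there, symptomatic ones included, in addition to the laboratory page.
- *That any rise that interrupts study drug is treated differently by the two sections.* Interruption is on neither AE list. The conflict concerns withdrawal and judged significance; a temporary interruption reaches 11.1 only through the significance criterion.
- *That the DSMB would not see the signal.* Section 5.1 lists clinically significant laboratory abnormalities among the safety assessments separately from TEAEs.

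Other safeguards also stand. Withdrawals are tabulated by reason with Kaplan-Meier curves (12.9.6), and the medical monitor reviews individual safety data and follows their capture in the eCRF (18.2.4). With the laboratory outputs, these make a partial backup. They do not put the event into the TEAE tables.

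**Conclusion.** The inconsistency is real and is in the current text. It matters for one kind of event: an asymptomatic, untreated laboratory abnormality that is judged clinically significant or leads to withdrawal. Such an event is an AE under 11.1 but need not be recorded as one under 10.2, so it may be missing from the TEAE tables and from discontinuations due to AEs.

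This rests on reading *i.e.* in 10.2 as a definition and on at least some sites working from that section. No number of lost events can be given. Counting combinations of criteria on which the two lists differ would not supply one, because the combinations are neither equally likely nor independent. The consequence is limited to AE and tolerability reporting. It is worth correcting because it is cheap to correct and the backup is incomplete at the visits where local laboratories may be used.

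Section 11.1 also has a separate filter for worsening of the disease under study, which could affect how an ALT rise is classified. That filter is not part of this conflict.

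**What to change.** 1. Keep one list. Delete the *i.e.* clause in 10.2 and refer to 11.1 for what counts as a laboratory AE. Add the therapy criterion from 10.2 to the 11.1 list so that no existing criterion is lost.
2. Have the sponsor state how a laboratory-driven interruption of study drug is to be recorded, since neither AE list mentions it. This is a recording question only; it sets no rule for dosing or stopping.
3. New text does not repair forms already completed. Before database lock, check every laboratory entry on the Comment CRF pages against the AE log using the single list, and query the gaps.

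The cost is a sentence in each section, a memo to sites and one query run. The downside is that somewhat more AEs will be recorded, in all arms.

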10.3 ECG

ECGs will be performed at weeks -4 - 0 (screening) visit (additional recording, up to 30 minutes apart will be performed if QTc is >450msec according to the machine output), week 24, week 52 (End-of-Treatment/Early Termination) and at any other time the investigator thinks it is necessary. Print-outs of the ECGs should be kept with the subject source document.

The subject should rest for at least 10 minutes before measurement is taken. Twelve-lead ECG should be performed following the subject being in a supine position for 5 minutes.

The ECG will be evaluated by the investigator at time of performance (signed and dated) and the printout should be kept in the source documentation file. These printouts may be sent by the Sponsor (or sites) to a central reading center at a later stage. When potentially clinically significant findings are detected by the Site Investigator, a cardiologist should be consulted for a definitive interpretation. All communications and diagnoses should be filed in the source documentation file. Protocol No: 005 ARREST study

The final decision whether the ECG findings are of clinical significance is under investigator responsibility/local cardiologist. The investigator's interpretation of the ECG will be recorded in the eCRF.

10.4 Pregnancy test

Pregnancy should be avoided during the study. Pregnancy test will be done to child bearing potential women. This test will be performed during the week -4 -0 (screening) visit and any other visit the investigator thinks it will be necessary.

Urine test maybe done at the Investigator's discretion (after the screening test) should only be recorded in the source documentation, unless the test results are positive (see Section 11.6).

10.5 Vital Signs

Vital signs (temperature, heart rate and blood pressure) will be completed at all scheduled and unscheduled visits.

Blood pressure and pulse will be recorded in a sitting position after resting for 5 minutes . All measurements will be recorded in the source documents.

Weight and waist circumference will be measured at screening, week 24 (visit 7), week 52 (End-of Treatment/Early Termination) and week 65 (follow up visit).

Height will be measured at week -4 - 0 (screening) visit only.

Information about the vital signs must be presented in the subject source documentation at the study site. Significant findings present prior to the start of the study medication treatment must be included in the relevant medical history or current medical history condition in the eCRF. Significant findings after the start of the study which meet the definition of an adverse event must be recorded in appropriate place in the eCRF.

10.6 Physical Examinations

Physical examination will be performed at weeks -4 - 1 (screening), visit 7, week 52 (End-of-Treatment/Early Termination) and at any time the investigator thinks it is necessary for the safety of the subject.

Information about the physical examination must be presented in the subject source documentation at the study site. Significant findings present prior to the start of the study medication treatment must be included in the relevant medical history or current medical history condition in the eCRF. Significant findings after the start of the study which meet the definition of an adverse event must be recorded in appropriate place in the eCRF.

11 SAFETY ASSESSMENTS AND PHARMACOVIGILANCE

Safety assessments will consist of evaluating relevant medical history, adverse events and serious adverse events, laboratory parameters including hematology, chemistry, vital signs, physical examinations, and documentation of all concomitant medications and/or therapies.

11.1 Adverse Event

An adverse event (AE) is defined as any untoward medical occurrence in a patient or clinical trial subject administered a medicinal product and which does not necessarily have a causal relationship with the treatment.

In the study, any event occurring after the clinical trial subject has signed the study Informed Consent should be recorded and reported as an AE.

An adverse event can therefore be any unfavorable and unintended sign (including an abnormal laboratory finding), symptom, or disease temporally associated with the use of an investigational medicinal product, whether or not considered related to the investigational medicinal product.

A new condition or the worsening of a pre-existing condition will be considered an AE. Stable chronic conditions such as arthritis that is present prior to study entry and do not worsen during the study will not be considered AE.

Worsening of the disease under study will be measured by laboratory test and clinical parameters should only be recorded as an AE if the outcome is more serious than would normally be expected from the normal course of the disease in a particular subject.

An abnormal result of diagnostic procedures including abnormal laboratory findings will be considered an AE if it:

- Results in subject's withdrawal by the investigator.
- Is associated with a serious adverse event (SAE).
- Is associated with clinical signs or symptoms.
- Is considered by the physician to be of clinical significance.

The intensity or severity of the AE will be characterized as:

Mild:AE which is easily tolerated.Moderate:AE sufficiently discomforting to interfere with daily activity.Severe:AE which prevents normal daily activities.

Unlabeled/ Unexpected AE - A reaction which is not included in the Adverse Reaction section of the relevant reference, including specificity, severity, outcome or frequency. The safety reference of this study is the Investigator's Brochure (IB).

TERMDEFINITIONCLARIFICATIONUnrelatedThis category applies to those
adverse events which, after
careful consideration, are

The relationship of an AE to the study drug is characterized as:

TERM	DEFINITION	CLARIFICATION
	clearly due to extraneous causes (disease, environment, etc.)	
Unlikely	In general, this category can be considered applicable to those adverse events, which after careful medical consideration at the time they are evaluated, are judged to be unrelated to the test drug.	 An adverse experience may be considered unlikely related if or when (must have two): It does not follow a reasonable temporal sequence from the administration of the test drug. It could readily have been produced by the subject's clinical state, environmental or toxic factors, or other modes of therapy administered to the subject. It does not follow a known pattern of response to the test drug. It does not reappear or worsen when the drug is readministered.
Possibly	This category applies to those adverse events for which, after careful medical consideration at the time they are evaluated, a connection with the test drug administration appears unlikely but cannot be ruled out with certainty.	 An adverse experience may be considered possibly related if or when (at least two of the following): It follows a reasonable temporal sequence from administration of the drug. It could not readily have been produced by the Subject's clinical state, environmental or toxic factors, or other modes of therapy administered to the Subject. It follows a known pattern of response to the test drug.
Probably	This category applies to those adverse events which, after careful medical consideration at the time they are evaluated, are felt with a high degree of certainty to be related to the test drug.	 An adverse experience may be considered probably related if or when (at least three of the following): It follows a reasonable temporal sequence from administration of the drug. It could not be reasonably explained by the known characteristics of the subject's clinical state, environmental or toxic factors or other modes of

TERM	DEFINITION	CLARIFICATION
		 therapy administered to the subject. It disappears or decreases on cessation or reduction in dose. There are important exceptions when an adverse event does not disappear upon discontinuation of the drug, yet drug-relatedness clearly exists. It follows a known pattern of response to the test drug.

The date of onset, a description of the AE, severity, seriousness, action taken, relationship to the study drug, outcome of the event and date of resolution will be recorded.

11.2 Serious Adverse Event

A Serious Adverse Event (SAE) is defined as an AE that results in any of the following:

- Death.
- Life-threatening.
- Requires hospitalization or prolongs existing inpatients' hospitalization.
- Results in persistent or significant disability or incapacity.
- Results in a congenital abnormality or birth defect.
- An important medical event which requires medical intervention to prevent any of the above outcomes.

Important medical events are those which may not be immediately life-threatening, but may jeopardize the subject and may require intervention to prevent one of the other serious outcomes listed above. Examples of such events are intensive treatment in an emergency room or at home for allergic bronchospasm; blood dyscrasias or convulsions that do not result in hospitalization; resulting in an adverse event will normally be considered serious by this criterion.

Inpatient **hospitalization** or prolongation of existing hospitalization means that hospital inpatient admission and/or prolongation of hospital stay were required for treatment of AE, or that they occurred as a consequence of the event. It does not refer to pre-planned elective hospital admission for treatment of a pre-existing condition that has not significantly worsened, or to diagnostic procedure.

The term **"life-threatening"** in the definition of "serious" refers to an event in which the patient was at risk of death at the time of the event; it does not refer to an event which hypothetically might have caused death if it were more severe.

Any new SAE that occurs after the study period and is considered to be related (possibly/probably) to the IMP or study participation should be recorded and reported immediately. The study period for the purpose of SAE reporting is defined as the period from the subject's signature on the informed consent form until the end of the follow-up period.

Events NOT considered to be SAEs are hospitalizations which:

- 1. Were planned before entry into the study.
- 2. Are for elective treatment of a condition unrelated to the indication or its treatment.
- 3. Occur on an emergency, outpatient basis and do not result in admission (unless fulfilling the criteria outlined above for a SAE).
- 4. Are part of the normal treatment or monitoring of the indication and not associated with any deterioration in condition .
- 5. Social reasons and respite care in the absence of any deterioration in the patient's general condition.

11.3 SAE Reporting

In order to satisfy regulatory requirements, any Serious Adverse Event, whether deemed IMPrelated or not, must be reported to the Local Clinical Management (CRA or sponsor representative) as soon as possible after the investigator or coordinator has become aware of its occurrence. The SAE form completion and reporting must not be delayed even if all of the information is not available at the time of the initial contact.

The SAE should be submitted within 24 hours of becoming aware of the event to the Local Clinical Management. The local Clinical Management will forward the report to which will handle all the safety reports.

Galmed have delegated responsibility for the safety management for this study to

SAE originated in this study should be sent to:

Additional information (follow-up) about any SAE unavailable at the initial reporting should be forwarded by the site within 24 hours of the information becoming available to the Local Clinical Management.

The following information should be provided on the SAE report form to accurately and completely record the event:

- 1. Investigator Name and Center Number.
- 2. Subject Number.
- 3. Subject initials.
- 4. Subject Demographics.
- 5. Clinical Event.
 - 1) Description.
 - 2) Date of onset.
 - 3) Severity.
 - 4) Treatment.
 - 5) Relationship to study drug (causality).
 - 6) Action taken regarding study drug.
- 6. If the AE result in Death.
 - 1) Cause of death (whether or not the death was related to study drug).
 - 2) Autopsy findings (if available).
- 7. Medical History case report form (copy).
- 8. Concomitant Medication case report form (copy).
- 9. Any relevant reports (laboratory, discharge, X-ray, etc).

Related SAEs *MUST* be collected and reported regardless of the time elapsed from the last study drug administration, even if the study has been closed.

Unrelated SAEs must be collected and reported during the study and up to the follow-up assessment.

For both initial and follow-up SAE reports the Local Clinical Management (CRA or sponsor representative) forwards this information to Diamond PV Services within 48 hours.

The blinding will be maintained for the people who are involved directly in the study, therefore in case of a SUSAR un-blinded information will not be forward to local study management or Galmed personnel.

This information should be sent to the Local Clinical Management who will forward the information to Diamond PV Services.

11.4 Safety reporting to Investigators, Institutional Review Boards or Independent Ethics Committees, and Regulatory Authorities.

The sponsor, via Diamond PV Services Ltd. is responsible for reporting all applicable SAEs to Regulatory authorities, Investigators, and IRBs/IECs, as applicable, in accordance with national regulations in the countries where the study is conducted.

For all investigators located in the European Economic Area, the sponsor via Diamond PV Services Ltd. will be responsible for reporting suspected unexpected adverse reactions (SUSARs) and any other applicable SAEs to regulatory authorities including the European Medicines Agency, Investigators, and IRB/IECs, as applicable, in accordance with national regulations in the countries where the study is conducted. The SUSARs will be submitted within 7 days for fatal and life-threatening events and within 15 days for other serious events.

In non-EU countries, SAEs will be reported to the regulatory authorities in accordance with local requirements by Diamond PV Services Ltd. SAEs should be reported by the site to their local EC/IRB as dictated by their board's policies and procedures.

Subjects who have had an SAE during the treatment period must be followed clinically until all parameters (including laboratory) have either returned to normal or have stabilized or are otherwise explained .

Any newly emergent SAEs after treatment is discontinued or the subject has completed the study and is considered to be related to the IMP or study participation should be recorded and reported immediately. The post-study period for the purpose of SAE reporting is routinely for up to 30 days following last visit of the study or until SAE is resolved or stabilized. In certain cases, such as where the drug has a long half-life, a longer follow-up period may be required.

